4.3.3 Handling of Study Drug

Kristalose is an FDA approved drug. We established an agreement with the manufacturer Cumberland to provide Kristalose supply. Kristalose will be distributed through Cumberland to the investigational drug pharmacy at Michigan Medicine. The study team will liaise with the investigational pharmacy and manufacturer to ensure that an adequate supply of drug is available for dispensing.

The investigational pharmacy is responsible for receipt, storage, dispensing, and reconciliation of the study drug. Pharmacy accountability will be monitored. The investigational pharmacy will maintain accountability logs for all supplies of Kristalose. These logs will include the purchase date (date received), lot number, expiration date, and quantity of all Kristalose supplied for the trial. In addition, every dose dispensed will also be recorded in a subject-specific accountability log. The Kristalose lot number for each dose dispensed will be recorded and the inventory balance will also be noted on the accountability log. Study drug shipping receipts will be retained. The investigational pharmacy will dispense 2 packages (30 20g dose packets in each package) of Kristalose to each subject randomized to the treatment group upon receipt of randomization notification either in person at Michigan Medicine or shipped directly to the patient via FedEx.

4.4 FOLLOW-UP AND OUTCOMES

The final follow-up study visit will occur 28 days post-baseline (SD 28±5). Primary and secondary outcome data will be collected at this visit. The SF-8, ANT and Health Follow-Up Questionnaire (see Appendix H) will be conducted with all subjects. The Health Follow-Up Questionnaire contains several questions from the baseline Health History Questionnaire including hospitalization data, overall sleep quality (PSQI), number of falls, number of bowel movements per day and regular daily activity impairment score (WPAI). This visit will be conducted via REDCap email and/or phone.

Table 1. Procedure Table

	Entry/ Day 1*	STUDY DAY						
		3	6	9	14	15	21	28 (SD 28 ± 5 days)
Informed Consent	X							
Randomization	X							
Contact Information	X							
Demographics Questionnaire	X							
Health History Questionnaire	X							
Short Form Health Survey 8	X							X
Animal Naming Test	X							X
AUDIT-C	X							
Health Follow-Up Questionnaire								X
Twilio/REDCap Email Automated Messages		X	X	X	X	X	X	X
Lactulose Therapy	X	X	→					X

* Control Group: Study Day 1 is defined as the calendar day on which the subject is randomized.

Treatment Group: Study Day 1 is defined as the calendar day on which the subject receives Kristalose.

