4. STUDY INTERVENTIONS AND PROCEDURES

4.1 ASSESSMENTS

4.1.1 Baseline Assessments

1. Demographics Questionnaire (DQ) (Appendix A)

Participants will be asked to provide the following demographic information:

1. Sex
2. Age
3. Ethnicity
4. Race
5. Highest education level attained
6. Marital status
7. Occupation status
8. Income
9. Rural/Urban residence

2. Health History Questionnaire (HHQ) (Appendix B)

Participants will be asked to provide the following information:

1. Cause of cirrhosis
2. History of liver cancer
3. Liver transplant waitlist status
4. Driving status
5. Disability status (Katz-ADL)
6. Hospitalization within past 90 days
7. Emergency Room visit within past 90 days
8. Ascites status
9. Currently taking diuretics
10. Paracentesis within past 90 days
11. Hepatic encephalopathy status
12. Medications taken for HE
13. Dialysis status
14. Diabetes status
15. Congestive heart failure status
16. Chronic obstructive pulmonary disease status
17. Overall sleep quality (*PSQI*)
18. Falls in past 4 weeks
19. Average number of bowel movements per day

3. Short Form-8 Health Survey (SF-8) (Appendix C)

The SF-8 is an abbreviated version of an original 36-item health survey (SF-36). It is a generic multipurpose quality of life instrument. It contains psychometrically based physical and mental

health summary measures. The eight domains include general health, physical functioning, role physical, bodily pain, vitality, social functioning, mental health and role emotional.

4. Animal Naming Test (ANT) (Appendix D)

The animal naming test is a timed test that consists of subjects listing as many unique animals as possible in 60 seconds. This is a validated test used for the assessment of hepatic encephalopathy.

5. Alcohol Use Disorders Identification Test-C (AUDIT-C) (Appendix E)

The AUDIT-C is a brief 3-item alcohol screening instrument that reliably identifies persons who are hazardous drinkers or have active alcohol use disorders.

4.1.2 28-Day Follow-Up Assessments

1. Health Follow-Up Questionnaire (HFUQ) (Appendix G)

Participants will be asked to provide the following information:

1. Hospitalizations during study period
2. Overall sleep quality (PSQI)
3. Falls during study period
4. Average number of bowel movements per day
5. Ability to do regular daily activities (WPAI)

2. Short Form-8 Health Survey (SF-8) (Appendix C)

3. Animal Naming Test (ANT) (Appendix D)

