4.2 ENROLLMENT PROCEDURES

4.2.1 Enrollment

After informed consent procedures, all subjects will complete enrollment procedures in the following order:

- a. Provide their contact information
- b. Randomization
- c. Baseline assessments
- d. Kristalose allocation and intervention counseling (*only if randomized to treatment group*)

In the control group, the date subjects are randomized and complete the baseline assessments is Study Day 1. These procedures can be conducted in person or via phone. In the treatment group, the date subjects receive Kristalose and receive intervention counseling is Study Day 1.

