3. SF-8
4. ANT
5. AUDIT-C

4.3 INTERVENTION PROCEDURES

4.3.1 Lactulose Administration and Duration

Subjects randomized to the control are not required to complete any intervention activities or treatments. For subjects randomized to lactulose therapy, the following steps to implement the intervention will occur on Study Day 1:

1. The Principal Investigator (PI) will prescribe lactulose to subjects enrolled at Michigan Medicine. Lactulose (Kristalose) will be allocated to the patient in person at the University of Michigan through the Investigational Pharmacy. If enrollment procedures were conducted remotely, the patient will be allowed up to two weeks to schedule an appointment with the study coordinator to receive Kristalose.
2. Subjects will be instructed to take 20g of Kristalose (1 packet) in 4oz water twice daily for 28 days. All patients randomized to lactulose will receive standard counselling.
3. First, all subjects will be instructed to take the first dose on awakening and the second dose approximately 4 hours after the first dose.
4. Second, subjects will be asked to monitor their bowel movements (see section 4.3.2 Adherence Assessment below). If they achieve ≥ 4 bowel movements in one day outside of the adherence assessments, they will be asked to contact the study team directly and will be instructed to reduce their lactulose frequency to one 20g dose daily. No dose adjustments will be made to *increase* bowel movements. Study staff will be alerted via email if a subject reports more than 4 bowel movements per day. Subjects will be instructed to call the study phone line if their bowel movements do not decrease with a reduced dose. They will also be instructed to notify the study team if they are undergoing proctoscopy or colonoscopy and to avoid taking nonabsorbable antacids (like aluminum or magnesium hydroxide) with Kristalose since these may interfere with the lactulose activity.
5. Third, patients will be counselled on the side effects of lactulose including mild bloating, cramping or diarrhea. If the symptoms worry the patient, they will be instructed to reduce lactulose to one 10g dose on awakening and then to increase to 10g twice daily as tolerated.

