4.1 If recently removed, how long ago was removal (in months): _____

4.2 If recently removed, specify reason for removal: _____

4. Have you stopped driving within the past 6 months?

 Yes	 Stopped driving more than 6 months ago
 No	

5. Are you dependent upon assistance from anyone for any of the following (check all that apply)?

 Bathing	 Getting out of bed or chair
 Dressing	 Eating
 Using the toilet/going to the bathroom	 None

6. Have you been hospitalized in the past 90 days?

No
 Yes

6.1 If yes, number of hospitalizations: 1 2 3 More than 3

7. Have you had an Emergency Room (ER) visit in the past 90 days?

No
 Yes

7.1 If yes, number of ER visits: 1 2 3 More than 3

8. Do you have ascites (accumulation of fluid in the abdomen)?

Yes
 No
 Unknown

9. Do you currently take diuretics/water pills (e.g. Lasix/Furosemide, Aldactone/Spironolactone)?

Yes
 No
 Unknown

10. Have you had a paracentesis (a procedure to remove fluid from the abdomen) within the last 90 days?

Yes
 No
 Unknown

11. Have you have a Transjugular intrahepatic portosystemic shunt (TIPS)?

Yes
 No
 Unknown

12. Are you currently receiving dialysis?

Yes
 No
 Unknown

13. Do you have diabetes?

Yes
 No
 Unknown

14. Do you have congestive heart failure (CHF)?

- Yes
- No
- Unknown

15. Do you have chronic obstructive pulmonary disease (COPD)?

- Yes
- No
- Unknown

16. During the past month, how would you rate your sleep quality overall?

- Very Good
- Fairly Good
- Fairly Bad
- Very Bad

17. Have you had any falls in the past 4 weeks?

- Yes
- No

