6.1 If yes, number of hospitalizations: _____

2. During the past month, how would you rate your sleep quality overall?

Very Good
 Fairly Good
 Fairly Bad
 Very Bad

3. Have you had any falls since you enrolled in this study?

Yes
 No

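### Follow-up falls are counted from enrolment, but Study Day 1 in the lactulose arm is drug receipt, so on one reading of the plan delayed lactulose subjects report falls over a longer window than controls

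*Combined protocol and SAP*

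**What the plan says.** **Start of the clock.** The Table 1 footnote in section 4.4 gives each arm its own start: "Control Group: Study Day 1 is defined as the calendar day on which the subject is randomized", and "Treatment Group: Study Day 1 is defined as the calendar day on which the subject receives Kristalose". Section 4.2.1 agrees for the lactulose arm: "In the treatment group, the date subjects receive Kristalose and receive intervention counseling is Study Day 1".

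**Lag to drug.** Section 4.2.1 puts randomization and the baseline assessments before Kristalose allocation. For remote enrolment, section 4.3.1 says "the patient will be allowed up to two weeks to schedule an appointment with the study coordinator to receive Kristalose". Section 4.3.3 has the pharmacy dispense "either in person at Michigan Medicine or shipped directly to the patient via FedEx". It gives no shipping time.

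**Falls items.** The follow-up form (Appendix G item 3) asks "Have you had any falls since you enrolled in this study". Section 4.1.2 labels the same item "Falls during study period". The baseline form (Appendix B item 17) asks "Have you had any falls in the past 4 weeks".

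**Timing of the final visit.** Table 1 places it at Study Day 28±5. The opening sentence of section 4.4 counts 28 days from baseline and equates this with Study Day 28±5. Section 1.2 counts 28 days from enrolment. Aim 6a compares falls from baseline to 28 days.

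**Analysis.** Section 6.2 treats every outcome as continuous, in a MANOVA with regression adjustment for baseline covariates. It mentions no time at risk.

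**The concern.** A count is comparable between arms only if both arms are observed for the same time, or if the analysis allows for the difference. Here the count starts at enrolment, while the visit that ends it is tied to a Study Day 1 that can come later in one arm only. Any extra days precede the first dose, so lactulose cannot have prevented falls in them. For a delayed subject the error runs against the drug.

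The text can also be read so that the falls windows are equal. On one such reading the problem moves to the length of treatment at the final visit, which is when the primary SF-8 is collected.

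**Working it through.** **Inputs from the documents.** Visit at 28 days, ±5 (section 4.4). Lag from enrolment to drug receipt: 0 in controls, nominally 0 to 14 days in remotely enrolled lactulose subjects (section 4.3.1). About 25 subjects per arm (section 2). I assume consent and randomization fall on the same day, as the single entry column of Table 1 suggests.

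**1. The plan's own figure.** With no lag, the window is 0 + 28 = 28 days, or 23 to 33 with the visit window. This holds for controls and for undelayed lactulose subjects.

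**2. Visit counted from Study Day 1, enrolment meaning consent or randomization.** Falls window = lag + 28.
- Lag 7: 7 + 28 = 35 days; 35/28 = 1.25.
- Lag 14: 14 + 28 = 42 days; 42/28 = 1.50. With ±5 the window is 37 to 47 days. The ratio is 47/33 = 1.42 if both visits are 5 days late and 37/23 = 1.61 if both are 5 days early.

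**3. The three readings, for a 14-day lag.**

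| Reading | Control falls window | Lactulose falls window | Days from drug receipt to visit |
|---|---|---|---|
| Visit from Study Day 1; enrolled at consent or randomization | 28 | 42 | 28 |
| Visit 28 days after enrolment, or after a baseline taken at randomization | 28 | 28 | about 14 |
| Visit from Study Day 1; enrolment includes Kristalose allocation | 28 | 28 | 28 |

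**4. Arm level, first reading, no drug effect.** Ratio of mean falls = 1 + pL/28, where p is the share delayed and L the lag. Neither is in the documents, so these values are assumed.
- 25%, 7 days: 1 + 1.75/28 = 1.06
- 50%, 7 days: 1 + 3.5/28 = 1.13
- 50%, 14 days: 1 + 7/28 = 1.25
- All, 14 days: 1 + 14/28 = 1.50

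**5. A rule that works the other way.** Section 5.3 brings the Day 28 assessments forward, to within 5 days, when lactulose stops early. That shortens the window in the lactulose arm only. If a share e loses D days, subtract eD/28. With an assumed 20% assessed at Day 14, this is 0.20 × 14/28 = 0.10, and the four ratios become 0.96, 1.03, 1.15 and 1.40. The two errors cancel when pL = eD.

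**6. Scale.** Assume 0.5 falls per 28 days and Poisson counts. The standard error of the mean difference is √(2 × 0.5/25) = 0.20 falls. Without early visits, the first three ratios in step 4 give biases of 0.031, 0.0625 and 0.125 falls, which are 0.16, 0.31 and 0.63 standard errors. The extreme row gives 0.25 falls, or 1.25 standard errors. An estimated ratio near 1 would have a 95% interval of exp(±1.96 × √(2/12.5)) = 0.46 to 2.19.

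**7. Dilution on the second reading.** With no drug effect the ratio is 1.00 at any lag. An assumed true on-drug ratio of 0.75 would appear as 0.75 + 0.25pL/28: 0.77 with 25% delayed 7 days, and 0.81 with 50% delayed 14 days.

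**The case against.** The strongest reply is that the plan never defines enrolment. Section 4.2.1 lists Kristalose allocation as the last enrolment procedure. A lactulose subject would then be enrolled only on receipt, and there would be no excess window. Table 1 shows consent, randomization, baseline forms and the start of lactulose in one entry column, with no lag. Section 1.2, Aim 6a and the opening sentence of section 4.4 can all be read as giving both arms 28 days. Lags may be short if drug is shipped promptly. Falls are an exploratory aim, and under most assumed inputs the bias is below one standard error.

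Much of this stands, and it limits how firmly the point can be put. It does not remove the point:
- Section 4.3.1 treats remote enrolment as already done before drug is received, so the plan uses the word in two ways. The subject filling in Appendix G is left to choose.
- Section 4.4 equates 28 days from baseline with Study Day 28. If baseline is taken at randomization, as the order in section 4.2.1 implies, the two agree only when there is no lag. If ±5 days is applied to both, Study Days 23 to 33 and days 23 to 33 after enrolment overlap only for lags of 10 days or less.
- On the post-enrolment reading, a subject with the full lag has only about 14 days on drug at the final visit.

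A reader might infer that the lactulose arm as a whole is observed for 42 days against 28, so that its falls are inflated by half. The documents do not support that. It would need every lactulose subject to be remote and delayed by 14 days. Nor is 42 a firm cap, because the two weeks are allowed for scheduling the appointment.

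**Conclusion.** The point holds conditionally. If the visit is counted from Study Day 1 and enrolment means consent or randomization, a lactulose subject with a 14-day lag reports falls over 42 days (37 to 47) against 28 (23 to 33) in a control, and the planned analysis does not correct for it. On the other two readings the falls windows are equal, but one of them halves the treatment time of a full-lag subject at the final visit. The passages conflict and must be reconciled.

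The arm-level ratio of 1.06 to 1.25 rests on assumed shares and lags. Early assessment under section 5.3 pulls the other way, so neither the net size nor the net direction of bias is established.

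A reader might also infer that the primary outcome is biased. The falls item does not touch it, because the SF-8 has a fixed four-week recall. Only on the post-enrolment reading would up to about 14 of those 28 days precede the drug.

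Falls are exploratory in Aim 6, though section 1.2 also lists them as secondary. For falls alone the consequence is limited. Severity: minor to moderate. Confidence: moderate.

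**What to change.** 1. In both arms, change Appendix G item 3 to ask for falls since the subject's own Study Day 1, with that date pre-filled. Analyse falls as a count, by Poisson or negative binomial regression, with log(actual days from that date to the visit) as offset. Apply this alike to visits inside the window and to early visits under sections 4.7, 4.8 and 5.3.
2. Record the dates of randomization, baseline forms, drug receipt and final visit for every subject.
3. Reconcile Aim 6a and sections 1.2, 4.2.1 and 4.4 on what the final visit is counted from, and define enrolment.

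Copying the four-week wording of the baseline form would be simpler but, with a fixed 28 days at risk, not sound. At a Day 23 visit, which is inside the window, about 5 of the 28 recalled days precede Study Day 1. A true ratio of 0.75 would then appear as (5 + 0.75 × 23)/28 = 0.79. The pre-filled date avoids this.

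The cost is one wording change, one analysis sentence and a few date fields. There are three drawbacks. Falls between randomization and drug receipt are not counted in the lactulose arm. The follow-up item no longer matches the four-week baseline item. The offset assumes a roughly constant fall rate and does not remove bias if stopping is related to falling.

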4.5 DISTINCT CLINICAL SCENARIO: PATIENT DEATH

In the event of a subject's death during the study period we will attempt to ascertain the date and cause of death, and hospitalization data that is available in the subject's Michigan Medicine electronic medical record.

4.6 DISTINCT CLINICAL SCENARIO: PATIENT HOSPITALIZATION

In the event of a subject's hospitalization during the study period, we will record the event as an Adverse Event (AE). If the subject's hospitalization coincides with study activities, we will revise each procedure as follows:

- 1) Lactulose therapy:** If a subject in the treatment group is hospitalized at Michigan Medicine during the study, the study PI and/or coordinator will contact the Michigan Medicine care team to discuss continuation of lactulose therapy during the hospitalization. If the hospitalization is a result of an AE from lactulose use, this will be discussed with the PI and lactulose may be paused or discontinued.
- 2) Follow-up phone study visits:** If the hospitalization coincides with the Day 28 follow-up visit, we will provide the subject an opportunity to reschedule the visit after discharge, under PI discretion.

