4.3.2 Adherence Assessment

During the 28-day intervention phase, all subjects will be contacted on Study Days 3, 6, 9, 14, 15, 21 and 28 via automated REDCap email or SMS text messages via Twilio service. Study Day 28 will only be collected via REDCap email or phone. These points of contact are to collect data about stool frequency and consistency among all subjects and therefore lactulose adherence in the treatment group. If the subject opts out of Twilio service, the subject can also receive these questions via REDCap automated email or a study coordinator will collect this data from the subject directly via phone or email. On Study Days 3, 6, 9, 14, 21 and 28 subjects will be asked the following questions:

1. "How many bowel movements did you have yesterday? Please respond with a whole number." *If 0-4 bowel movements are reported the subject will exit the survey. If >4, the subject will receive the following instructions:*

Since you had > 4 bowel movements yesterday, please reduce to **one** 20g dose of kristalose (1 packet) packet per day. Please call the study line at [contact] if you continue to have more than 4 bowel movements daily or with any questions or concerns.

On Study Day 15 subjects will be asked:

2. "Please reference the Bristol Stool Chart we provided to you to answer this question. How would you describe your stool looks today? Please respond with the applicable number, between 1-7. *All subjects exit survey after response.*

1. Separate hard lumps
2. Sausage-shaped but lumpy
3. Like a sausage but with cracks on its surface
4. Like a sausage or snake, smooth and soft
5. Soft blobs with clear cut edges
6. Fluffy pieces with ragged edges, a mushy stool
7. Watery, no solid pieces, entirely liquid

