5.2 ADVERSE AND SERIOUS ADVERSE EVENT DEFINITIONS & REPORTING

5.2.1 Adverse and Serious Adverse Event Definitions (AE & SAE)

In the Mi-Kristal study an AE is defined as any untoward or unfavorable physical, social or psychological occurrence in a participant that can be temporally associated with the subject's participation in the study, whether or not considered directly related to the subject's participation in the research. An AE is considered an SAE if the event results in death or permanent disability and is definitely related to the subject's participation in the study. However, due to the nature of the participants enrolled and low risk nature of the treatments, the AEs and SAEs recorded and reported to the IRB will be limited using the following guidance.

All hospitalizations will be reported as AEs. Other events that are not attributable to their participation in the study will not be reported as AEs, even if the data are collected for study purposes (e.g. car accident, stroke, myocardial infarction etc.). The exception to this standard is death, which will always be reported as either an AE or SAE. Additionally, expected clinical issues that subjects experience related to their ongoing medical care or chronic health problems will not be considered AEs unless it involves any of the above mentioned AE examples. Any AEs that are attributable to the study will be reported and adhere to the AE Reporting Timeline (see Table 3 below). The 28 ± 7 days end point is our final contact with subjects in which we will collect AE and SAE information. Events which qualify as AEs will be classified using the following IRB standards:

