Appendix G. Health Follow-Up Questionnaire**Mi-Kristal Trial Follow-Up Health Questionnaire**

Instructions: Please answer the following questions to the best of your knowledge. Please record the date the form was completed on the top of this page.

1. Have you been hospitalized since you enrolled in this study?

No
 Yes

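### Every hospitalization must be recorded as an adverse event, but subjects are asked about admission only on the Day 28 or early-termination form, so an admission outside Michigan Medicine has no planned route to the PI during treatment

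*Combined protocol and SAP*

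**What the plan says.** **What must be captured.** Section 4.6 opens by recording any subject's admission as an adverse event (AE). Section 5.2.1 agrees: "All hospitalizations will be reported as AEs". Neither is limited by hospital.

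**What follows from an admission.** Item 1 of 4.6 begins with a step limited by site: "If a subject in the treatment group is hospitalized at Michigan Medicine during the study, the study PI and/or coordinator will contact". That contact is with the treating clinicians at that hospital and concerns whether lactulose goes on. The next sentence of item 1 takes an admission caused by lactulose to the PI, with a pause or discontinuation possible, and names no hospital. Item 2, on rescheduling the final visit, names none either.

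**When subjects are asked.** Treatment lasts four weeks: "Subjects will be instructed to take 20g of Kristalose (1 packet) in 4oz water twice daily for 28 days". Of the contacts during that time, 4.3.2 says "These points of contact are to collect data about stool frequency and consistency among all subjects". Days 3, 6, 9, 14, 21 and 28 ask for a stool count and Day 15 asks for a stool type. The only in-study question on admission is item 1 of the Health Follow-Up Questionnaire (Appendix G), "Have you been hospitalized since you enrolled in this study", answered yes or no with a count. Section 4.4 and Table 1 place that form at Day 28±5. Sections 4.7 and 4.8 also request it at early termination. Under 4.8, a subject who declines it leaves the study at once.

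**Other routes.** The counselling in 4.3.1 asks subjects to call about stools and to mention a planned proctoscopy or colonoscopy. It does not mention admissions. After a death, 4.5 seeks "hospitalization data that is available in the subject's Michigan Medicine electronic medical record". No record search is stated for anyone else.

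**The concern.** The PI discussion in 4.6 is useful during treatment only if the team hears of the admission while the subject is still taking the drug. The plan sets the duty to record and the duty to discuss, but gives no scheduled means of finding out before the final or early-termination form.

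Admissions elsewhere are foreseeable. Section 3.3.1 speaks of several centers and of recruitment by email, and 4.2.1 allows enrollment procedures by phone. Section 4.3.3 allows drug to be "shipped directly to the patient via FedEx", although 4.3.1 describes collection in person, so how common remote supply will be is unclear.

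Two things are at stake. One is timely review of a possibly drug-related admission. The other is a complete count of admissions in both arms, which 5.2.1 requires and which depends on a form that a very ill or withdrawn subject may not complete.

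**Working it through.** The plan states no figure on this point, so there is none to reproduce. The check compares schedules and then does simple arithmetic on them.

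**1. Contacts that ask about admission.** The contacts before the final window opens are Days 3, 6, 9, 14, 15 and 21 (4.3.2). Contacts asking about admission: 0 of 6.

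**2. Position of the form.** 28 − 5 = Day 23 and 28 + 5 = Day 33, against a 28-day course. At Day 23 up to 5 treatment days are still to come; at Day 33 the scheduled course ended 5 days earlier. Section 5.2.1 gives 28±7 for the last AE contact, that is Day 21 to Day 35, which does not match 4.4.

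**3. Mean delay to detection.** Assumptions: admissions are uniform over days 0 to 28, nobody reports one unprompted, and every contact is answered. For contact intervals of length L, the mean delay is ΣL² / (2 × 28).

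- One question at Day 28: 28² / 56 = 14.0 days.
- Question at Days 3, 6, 9, 14, 21 and 28 (intervals 3, 3, 3, 5, 7, 7): (9 + 9 + 9 + 25 + 49 + 49) / 56 = 150 / 56 = 2.7 days.
- Effect of the window: a form answered at Day 33 gives 33 − 14 = 19 days. A form answered at Day 23 gives 23 / 2 = 11.5 days for earlier admissions, and leaves those in the last 5 of 28 days (18%) unasked.

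**4. Subjects without the form.** Section 2 allows up to 75 enrolled for 50 completers: 75 − 50 = 25, or 33%, about 12 to 13 per arm. This is a ceiling, not a forecast. The documents give no admission rate, so p below is assumed. If none of m = 12 to 13 treated non-completers fills in the form, the chance of at least one unasked admission is 1 − (1 − p)^m:

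| Assumed 28-day risk p | m = 12 | m = 13 |
|---|---|---|
| 5% | 0.460 | 0.487 |
| 10% | 0.718 | 0.746 |
| 20% | 0.931 | 0.945 |

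These are upper limits, because withdrawing subjects are asked for the form (4.8) and deaths lead to a record search (4.5).

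**5. Whether another section closes the gap.** Section 5.3 stops the intervention after a possibly related SAE, but 5.2.1 defines an SAE as death or permanent disability that is definitely related. An admission alone does not qualify. Section 5.3 also moves the Day 28 assessments to within 5 days of stopping lactulose, and no later admission question is stated for that subject.

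**The case against.** Several stronger readings are tempting, and the text does not support them.

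- **That 4.6 acts only on Michigan Medicine admissions.** Only the care-team contact carries that limit. The AE recording, the PI discussion and the rescheduling do not.
- **That an outside admission cannot lead to review during treatment.** If the subject or a relative calls, 4.6 provides for PI discussion. What is missing is a planned prompt.
- **That the question is put only around the last dose.** The same form is requested at early termination, which can come much earlier.
- **That hospitalization is the trial's main between-arm safety measure.** Section 1.1.3 names more than five daily stools and falls as the adverse-event aims. Hospitalization is neither an aim nor an endpoint.
- **That a number of lactulose-related admissions would be missed.** The documents give no admission rate, no share admitted elsewhere and no drug-related fraction. Any such count would be assumption throughout.

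It can also be said that this is a 28-day study of about 50 patients on an approved drug, that the consent form is not among the documents and may tell subjects to report admissions, and that 5.2.1 calls the last visit the final contact for AE information, which could imply earlier enquiry. These points lower the urgency. They do not supply a scheduled question: the contacts that 4.3.2 lists are confined to stools, and 7.4 confines the Twilio messages to bowel-movement responses.

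**Conclusion.** The point holds as a gap in ascertainment. The plan requires all admissions to be recorded and drug-related ones to be discussed with the PI, but asks about admission only on the final or early-termination form. An admission outside Michigan Medicine has no planned route to the PI during treatment, and any admission can be missed in a subject who does not complete the form.

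The size is a mean delay of 14 days instead of about 2.7, under uniform timing, no spontaneous reporting and full response to messages. Volunteered reports would shorten the 14 days; unanswered messages, including those sent to a subject in hospital, would lengthen the 2.7. The table for non-completers is illustrative only. The primary SF-8 comparison is not affected. The change is worth making because it is cheap, not because harm has been shown.

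**What to change.** 1. Add one yes/no item to the existing contacts in both arms, asking about any hospital stay since the last contact, and send a yes to the staff email alert already used for high stool counts (4.3.1). Place it before the point where a subject reporting 0 to 4 stools leaves the survey. State that controls receive the contacts: 4.3.2 says all subjects do, but the Summary and 7.4 mention only treated subjects.
2. Send the item by REDCap email or phone. If Twilio is used, revise 7.4, which limits its content to bowel-movement responses and excludes PHI.
3. At Day 1, ask subjects in both arms to tell the study team of any admission.
4. For subjects without a completed Day 28 form, check the Michigan Medicine record for admissions through Day 28, as far as consent and 4.8 allow. This cannot find admissions elsewhere, so items 1 and 3 matter most.
5. Reconcile the site-limited sentence in 4.6 item 1 with the unrestricted sentences in 4.6 and 5.2.1, and the ±5 window with the ±7 window. Any decision about the drug stays with the PI.

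The cost is slightly more subject burden, a few record checks, and wording changes in 4.3.1, 4.3.2, 4.6, 4.8 and, if Twilio carries the item, 7.4.
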